4.0 PATIENT ELIGIBILITY

Important note: The eligibility criteria listed below are interpreted literally and cannot be waived. All clinical and laboratory data required for determining eligibility of a patient enrolled on this trial must be available in the patient's medical or research record which will serve as the source document for verification at the time of audit.

Laboratory Studies:

All laboratory studies to determine eligibility must be performed within 7 days prior to enrollment unless otherwise indicated.

Laboratory values used to assess eligibility must be no older than seven (7) days at the start of therapy. Laboratory tests need **not** be repeated if therapy starts **within** seven (7) days of obtaining labs to assess eligibility.

If a post-enrollment lab value is outside the limits of eligibility, or laboratory values are older than 7 days, then the following laboratory evaluations must be re-checked within 48 hours prior to initiating therapy: CBC with differential, bilirubin, ALT (SGPT), albumin and serum creatinine. If the recheck is outside the limits of eligibility, the patient may not receive protocol therapy and will be considered off protocol therapy.

Clinical Studies:

All clinical studies to determine eligibility must be performed within 7 days prior to enrollment unless otherwise indicated. Imaging studies must be obtained within 14 days prior to enrollment (repeat the tumor imaging if necessary).

Clarification in timing when counting days: As an example, please note that if the patient's last day of prior therapy is September 1st, and the protocol requires waiting at least 7 days for that type of prior therapy, then that patient cannot be enrolled until September 8th.

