4.1.7 Disease Status:4.1.7.1 Part A: Patients must have either measurable or evaluable disease.4.1.7.2 Part B (1, 2, 3): Patients must have measurable disease.

THIS PROTOCOL IS FOR RESEARCH PURPOSES ONLY, SEE PAGE 1 FOR USAGE POLICY

4.1.7.3 **CNS Metastases:** Patients with a prior history of CNS metastases may enroll on study, provided there is no current evidence of active disease at the time of enrollment.

4.1.8 **Therapeutic Options:**

Patient's current disease state must be one for which there is no known curative therapy or therapy proven to prolong survival with an acceptable quality of life.

4.1.9 **Performance Level:**

Patients must have a performance status corresponding to ECOG scores of 0, 1 or 2. Use Karnofsky $\geq 50\%$ for patients > 16 years of age and Lansky $\geq 50\%$ for patients ≤ 16 years of age. Note that neurologic deficits in patients with tumors previously metastatic to the CNS (or other non-oncologic reasons) must have been stable for at least 7 days prior to study enrollment. Patients who are unable to walk because of paralysis, but who are up in a wheelchair, will be considered ambulatory for the purpose of assessing the performance score.

See https://www.cogmembers.org/site/pages/default.aspx?page=Prot_reference_materials under Standard Sections for Protocols.

4.1.10 **Prior Therapy:**

4.1.10.1 Patients must have fully recovered from the acute toxic effects of all prior anti-cancer therapy and must meet the following minimum duration from prior anti-cancer directed therapy prior to enrollment. If after the required timeframe, the numerical eligibility criteria are met, e.g., blood count criteria, the patient is considered to have recovered adequately.

- a. **Cytotoxic chemotherapy or other anti-cancer agents known to be myelosuppressive:** ≥ 21 days after the last dose of myelosuppressive chemotherapy (42 days if prior nitrosourea). See DVL homepage on the COG Members site for commercial and investigational agent classifications. For agents not listed, the duration of this interval must be discussed with the study chair and the study-assigned Research Coordinator prior to enrollment. Refer here for details: <https://www.cogmembers.org/uploadedFiles/Site/Disc/DVL/Documents/TableOfMyelosuppressiveAnti-CancerAgents.pdf>

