- b. **Anti-cancer agents not known to be myelosuppressive (eg, not associated with reduced platelet or ANC counts):** ≥ 7 days after the last dose of agent. See the DVL homepage on the COG Members site for commercial and investigational agent classifications. For agents not listed, the duration of this interval must be discussed with the study chair and the study-assigned Research Coordinator prior to enrollment.
- c. **Antibodies:** ≥ 21 days must have elapsed from infusion of last dose of antibody, and toxicity related to prior antibody therapy must be recovered to Grade ≤ 1 .
- d. **Corticosteroids:** See [Section 4.2.2.1](#). If used to modify **immune adverse events** related to prior therapy, ≥ 14 days must have elapsed since last dose of corticosteroid.
- e. **Hematopoietic growth factors:** ≥ 14 days after the last dose of a long-acting growth factor (e.g., pegfilgrastim) or 7 days for short-acting growth factor. For agents that have known adverse events occurring beyond 7 days after administration, this period must be extended beyond the time during which adverse events are known to occur.

THIS PROTOCOL IS FOR RESEARCH PURPOSES ONLY, SEE PAGE 1 FOR USAGE POLICY

f. Interleukins, Interferons and Cytokines (other than Hematopoietic Growth Factors): ≥ 21 days after the completion of interleukins, interferon or cytokines (other than Hematopoietic Growth Factors)

g. Stem cell Infusions (with or without TBI):

- Allogeneic (non-autologous) bone marrow or stem cell transplant, or any stem cell infusion including donor lymphocyte infusions (DLI) or boost infusion: ≥ 84 days after infusion and no evidence of GVHD.
- Autologous stem cell infusion including boost infusion: ≥ 30 days.

h. Cellular Therapy: ≥ 42 days after the completion of any type of cellular therapy (e.g., modified T cells, NK cells, dendritic cells, etc.).

i. XRT/External Beam Irradiation including Protons: ≥ 14 days after local XRT; ≥ 150 days after TBI, craniospinal XRT or if radiation to $\geq 50\%$ of the pelvis; ≥ 42 days if other substantial BM radiation.

j. Radiopharmaceutical therapy (eg, radiolabeled antibody, ^{131}I -MIBG): ≥ 42 days after systemically administered radiopharmaceutical therapy.

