APPENDIX XIII: RESPONSE CRITERIA FOR SOLID TUMORS

Disease Parameters

- **Measurable disease:** Measurable lesions are defined as those that can be accurately measured in at least one dimension (longest diameter to be recorded) as ≥ 20 mm by chest x-ray, as ≥ 10 mm with CT scan, or ≥ 10 mm with calipers by clinical exam. All tumor measurements must be recorded in millimeters (or decimal fractions of centimeters).

NOTE: Tumor lesions that are situated in a previously irradiated area might or might not be considered measurable. If the investigator thinks it appropriate to include them, the conditions under which such lesions should be considered must be defined in the protocol.

- **Malignant lymph nodes:** To be considered pathologically enlarged and measurable, a lymph node must be ≥ 15 mm in short axis when assessed by CT scan (CT scan slice thickness no greater than 5 mm). At baseline and in follow-up, only the short axis will be measured and followed.
- **Non-measurable disease:** All other lesions (or sites of disease), including small lesions (longest diameter < 10 mm) or pathological lymph nodes with ≥ 10 to < 15 mm short axis, are considered non-measurable disease. Bone lesions, leptomeningeal disease, ascites, pleural/pericardial effusions, lymphangitis cutis/pulmonitis, inflammatory breast disease, and abdominal masses (not followed by CT or MRI), are considered as non-measurable.

NOTE: Cystic lesions that meet the criteria for radiographically defined simple cysts should not be considered as malignant lesions (neither measurable nor non-measurable) since they are, by definition, simple cysts. "Cystic lesions" thought to represent cystic metastases can be considered as measurable lesions, if they meet the definition of measurability described above. However, if non-cystic lesions are present in the same patient, these are preferred for selection as target lesions.

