- **Target lesions:** All measurable lesions up to a maximum of 2 lesions per organ and 5 lesions in total, representative of all involved organs, should be identified as target lesions and recorded and measured at baseline. Target lesions should be selected on the basis of their size (lesions with the longest diameter), be representative of all involved organs, but in addition should be those that lend themselves to reproducible repeated measurements. It may be the case that, on occasion, the largest lesion does not lend itself to reproducible measurement in which circumstance the next largest lesion that can be measured reproducibly should be selected. A sum of the diameters (longest for non-nodal lesions, short axis for nodal lesions) for all target lesions will be calculated and reported as the baseline sum diameters. If lymph nodes are to be included in the sum, then only the short axis is added into the sum. The baseline sum diameters will be used as reference to further characterize any objective tumor regression in the measurable dimension of the disease.
- **Non-target lesions:** All other lesions (or sites of disease) including any measurable lesions over and above the 5 target lesions should be identified as non-target lesions and should also be recorded at baseline. Measurements of these lesions are not required, but the presence, absence, or in rare cases unequivocal progression of each should be noted throughout follow-up.

Methods for Evaluation for Patients with Solids Tumors and Measurable Disease

All measurements should be taken and recorded in metric notation using a ruler or calipers.

The same method of assessment and the same technique should be used to characterize each identified and reported lesion at baseline and during follow-up. Imaging-based evaluation is preferred to evaluation by clinical examination unless the lesion(s) being followed cannot be imaged but are assessable by clinical exam.

THIS PROTOCOL IS FOR RESEARCH PURPOSES ONLY, SEE PAGE 1 FOR USAGE POLICY

- **Clinical lesions:** Clinical lesions will only be considered measurable when they are superficial (eg, skin nodules and palpable lymph nodes) and ≥ 10 mm diameter as assessed using calipers (eg, skin nodules). In the case of skin lesions, documentation by color photography, including a ruler to estimate the size of the lesion, is recommended.

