 - No FDG-PET at baseline and a positive FDG-PET at follow-up: If the positive FDG-PET at follow-up corresponds to a new site of disease confirmed by CT, this is PD. If the positive FDG-PET at follow-up is not confirmed as a new site of disease on CT, additional follow-up CT scans are needed to determine if there is truly progression occurring at that site (if so, the date of PD will be the date of the initial abnormal FDG-PET scan). If the positive FDG-PET at follow-up corresponds to a pre-existing site of disease on CT that is not progressing on the basis of the anatomic images, this is not PD.

Note: A "positive" FDG-PET scan lesion means one that is FDG avid with an uptake greater than twice that of the surrounding tissue on the attenuation corrected image.

Response Criteria for Patients with Solid Tumors and Evaluable Disease

Evaluation of Target Lesions:

- **Complete Response (CR):** Disappearance of all target and non-target lesions. Any pathological lymph nodes (whether target or non-target) must have reduction in short axis to <10 mm. If immunocytology is available, no disease must be detected by that methodology. Normalization of urinary catecholamines or other tumor markers if elevated at study enrollment (for patients with neuroblastoma).
- **Partial Response (PR):** At least a 30% decrease in the sum of the diameters of target lesions, taking as reference the baseline sum diameters
- **Progressive Disease (PD):** At least a 20% increase in the sum of the diameters of target lesions, taking as reference the smallest sum on study (this includes the baseline sum if that is the smallest on study). In addition to the relative increase of 20%, the sum must also demonstrate an absolute increase of at least 5 mm. (Note: the appearance of one or more new lesions is also considered progressions). Note: In presence of SD or PR in target disease but unequivocal progression in non-target or non-measurable disease, the patient has PD if there is an overall level of substantial worsening in non-target disease such that the overall tumor burden has increased sufficiently to merit discontinuation of therapy
- **Stable Disease (SD):** Neither sufficient shrinkage to qualify for PR nor sufficient increase to qualify for PD, taking as reference the smallest sum diameters while on study

Evaluation of Non-Target Lesions

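### Appendix XIII requires conditions for counting previously irradiated lesions as measurable, but the available text gives none, so radiation shrinkage is not clearly kept out of confirmed response

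*Combined protocol and SAP*

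**What the plan says.** The definition of measurable disease in Appendix XIII carries a note: "Tumor lesions that are situated in a previously irradiated area might or might not be considered measurable". If the investigator wishes to include them, it continues, "the conditions under which such lesions should be considered must be defined in the protocol".

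The other provisions that bear on this are:

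- **Section 4.1.7.2 (Part B):** "Patients must have measurable disease". Radiation history is not mentioned.
- **Section 4.1.10.1, item i:** a patient-level interval of "≥ 14 days after local XRT", with longer intervals for larger fields. No condition applies to individual lesions.
- **Section 4.0:** "Imaging studies must be obtained within 14 days prior to enrollment".
- **Appendix XIII, target lesions:** "All measurable lesions up to a maximum of 2 lesions per organ and 5 lesions in total, representative of all involved organs", chosen on size, organ representation and reproducibility.
- **Appendix XIII, partial response:** "At least a 30% decrease in the sum of the diameters of target lesions, taking as reference the baseline sum diameters".
- **Sections 8.4.1 and 12.2.1.2:** responders' scans are reviewed centrally. No criterion for irradiated lesions is given.
- **Section 12.2:** refers the reader to RECIST 1.1 and back to Appendix XIII.

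**The concern.** The protocol sets itself a requirement that its available text does not meet. A site holding a recently irradiated measurable lesion cannot tell from the document whether it may be a target lesion. Two sites could decide differently, and so could a site and the central reader.

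Confirmed response is what decides Part B, and the thresholds are low. In B1 and B2 (Section 11.5), one response among 10 patients opens stage 2, and 3 among 20 leads to the conclusion that the agent is effective. If shrinkage from radiotherapy given before enrollment counts as a response to the drug, a single such case can carry a cohort past its futility stop.

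**Working it through.** **1. Where a rule could sit.** Sections 4.0, 4.1.7, 4.1.10.1, 8.4.1, 12.2 and 12.2.1.2 and the target-lesion paragraph of Appendix XIII contain no lesion-level condition on prior radiation. Section 12.2 says Appendix XIII also holds imaging guidelines for Ewing sarcoma, PAX3-FOXO1 ARMS and DDR. None is visible, and some pages after the visible end of that appendix were not available. Absence is therefore judged on the available text only.

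**2. Timing under the protocol's own windows.**

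- Local radiotherapy may end 14 days before enrollment, and the baseline scan may be up to 14 days before enrollment. Minimum gap from last radiotherapy to baseline scan: 14 − 14 = 0 days.
- Treatment starts 0 to 5 days after enrollment (Section 3.8). The first disease evaluation is in the last week of cycle 1 (Section 8.1), days 22 to 28, which is 21 to 27 days after day 1.
- For radiotherapy ending 14 days before enrollment, the first response scan falls between 14 + 0 + 21 = 35 and 14 + 5 + 27 = 46 days after it ended.

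The baseline sum can thus be fixed directly after radiotherapy, with response read five to seven weeks later. Section 7.1 bars radiotherapy during treatment, so only radiotherapy before enrollment is at issue.

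**3. The plan's own figures for B1/B2.** With response probability p, stop after stage 1 if there are 0 responses in 10; declare activity if there are 3 or more in 20:

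P(declare) = P(X₂₀ ≥ 3) − P(X₁₀ = 0) × P(X₁₀ ≥ 3).

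At p = 0.05:

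- P(X₂₀ ≥ 3) = 0.0755
- P(X₁₀ = 0) = 0.95¹⁰ = 0.5987
- P(X₁₀ ≥ 3) = 0.0115
- P(declare) = 0.0755 − 0.5987 × 0.0115 = 0.0686
- Expected size = 10 + (1 − 0.5987) × 10 = 14.0

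At p = 0.25 the same formula gives 0.882. The plan states 7%, 60% early termination, an expected size of 14, and 88% power. All agree.

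**4. Illustration A: a slightly raised apparent null rate.** The documents give no frequency for radiation-driven response, so this is an assumption. If a share q of true non-responders is classed as responding, the apparent rate is 0.05 + 0.95q. An apparent rate of 6% needs q = 0.01/0.95, about 1.05%.

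At p = 0.06:

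- P(X₂₀ ≥ 3) = 0.1150
- P(X₁₀ = 0) = 0.94¹⁰ = 0.5386
- P(X₁₀ ≥ 3) = 0.0188
- P(declare) = 0.1150 − 0.5386 × 0.0188 = 0.105

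Over a wider assumed range, B1/B2 type I error is:

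| q | Type I error |
|---|---|
| 0 | 6.9% |
| 1% | 10.3% |
| 2% | 14.3% |
| 3% | 18.7% |
| 5% | 28.5% |

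**5. Illustration B: one radiation-driven responder in stage 1.** This conditions on the event and needs no assumed frequency. The futility stop can no longer occur, and activity is declared if 2 or more of the other 19 patients respond. At 5%:

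1 − 0.95¹⁹ − 19 × 0.05 × 0.95¹⁸ = 1 − 0.3774 − 0.3774 = 0.245.

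**The case against.** The strongest reply is textual. The note makes inclusion depend on conditions set in the protocol. If none are set, the precondition is unmet and such lesions are excluded. Section 4.0 adds that eligibility criteria are read literally and cannot be waived. A reader might therefore go too far in inferring that the protocol permits recently irradiated target lesions. It does not say so. Nor does it say they are barred, and that ambiguity is what remains.

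Several rules also narrow the path:

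- The 30% fall applies to the sum over up to five target lesions, so an irradiated lesion must dominate that sum.
- New lesions, or unequivocal progression of non-target disease, make the patient a progressor whatever the irradiated lesion does.
- Bone lesions are non-measurable and cannot be targets.
- Responses need confirmation and central review.

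These points stand and make the event less likely. None of them looks at radiation history, however. Radiation shrinkage can persist to a confirmatory scan, and Section 8.4.1 sends central readers imaging, not radiotherapy site or date.

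A reader might also infer from the upper rows of the table that the real type I error is several times the stated one. The documents do not support that: no value of q can be drawn from them. B3 adds little weight. It is a secondary aim, is labeled non-statistical in Section 4.1.5.2, and uses its two-stage rule only if enrollment suffices.

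**Conclusion.** The point holds as an unfinished response rule. The available text does not say whether previously irradiated lesions may be target lesions, although Appendix XIII says the conditions must be defined. On the permissive reading, nothing in that text stops a lesion irradiated just before the baseline scan from entering the target sum.

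The stated operating characteristics are right; what is unprotected is the response count they are applied to. The size of the effect is unknown. The rise from 6.9% to 10.5% rests on an assumed apparent null rate of 6%. The 24.5% applies only if one stage 1 responder is radiation-driven and the other 19 patients respond at 5%. Both show how sensitive the rule is to one or two misattributed responses; neither estimates what will happen. The conclusion also assumes that the unavailable pages contain no such rule. This should be corrected, because the decision thresholds are low and the correction is small.

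**What to change.** Replace the note in Appendix XIII with an explicit rule: a lesion in a previously irradiated field may be a target lesion only if progression at that site was documented after radiotherapy ended; otherwise it is recorded as non-target. Record radiotherapy site and date for baseline lesions, and supply them to central review so that it applies the same rule. Apply the rule also to Part A patients who are counted in the Phase 2 evaluation under Section 11.5, since they must meet Part B eligibility.

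The cost is more than the sentence itself. No item in the Section 8.1 schedule collects lesion-level radiotherapy history, so a small data item is needed. A few patients whose only measurable lesion was recently irradiated would not qualify for Part B.

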12.2.1 Definitions**12.2.1.1 Evaluable for toxicity:**

All patients who experience a cycle 1 DLT or receive at least 75% of the planned dose will be evaluable for toxicity from the time of their first treatment with BAY 1895344 (elimusertib). Enrolled patients who have not received any treatment will not be considered evaluable for toxicity.

12.2.1.2 Evaluable for objective response:

All patients who receive at least one dose of BAY 1895344 (elimusertib) will be evaluable for response. Evaluable patients who demonstrate a complete or partial response confirmed by central review before receiving non-protocol anti-cancer therapy will be considered a responder. All other evaluable patients will be considered non-

responders. The evaluation period for determination of the best response will be 6 treatment cycles. All patients considered to have a response (CR or PR) must have imaging studies reviewed centrally. Centers will be notified by the PEP-CTN about requests for scans of patients with CR, PR, or long-term stable disease. See [Section 8.4](#) regarding shipping instructions.

12.2.1.3 Evaluable Non-Target Disease Response:

Eligible patients who have lesions present at baseline that are evaluable but do not meet the definitions of measurable disease and have received at least one dose of protocol therapy will be considered evaluable for non-target disease. The response assessment is based on the presence, absence, or unequivocal progression of the lesions.

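### Appendix XIII conflicts with itself on bone lesions: it does not say whether one with a soft-tissue mass of 10 mm or more on CT is measurable, which affects Part B entry and the scoring of PR

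*Combined protocol and SAP*

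**What the plan says.** **Two rules in Appendix XIII, under Disease Parameters**

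- Measurable disease: "Measurable lesions are defined as those that can be accurately measured in at least one dimension". The size limits are 20 mm by chest x-ray, 10 mm by CT and 10 mm by calipers. No limit is given for MRI, although the methods part of the appendix accepts MRI in some situations.
- The bullet on what does not qualify: "Bone lesions, leptomeningeal disease, ascites, pleural/pericardial effusions, lymphangitis cutis/pulmonitis, inflammatory breast disease, and abdominal masses (not followed by CT or MRI), are considered as non-measurable". A note then lets cystic metastases count as measurable if they meet the general definition. There is no matching note for bone.

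**What depends on these rules**

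- Section 4.1.7.2, for B1, B2 and B3: "Patients must have measurable disease". Section 4.0 says that eligibility criteria are applied to the letter, with no waivers.
- Target lesions come from "All measurable lesions up to a maximum of 2 lesions per organ and 5 lesions in total". All other lesions are non-target: "Measurements of these lesions are not required".
- PR is "At least a 30% decrease in the sum of the diameters of target lesions", relative to baseline. With evaluable-only disease, the appendix does not allow a PR.
- Section 12.2.1.2: "All patients who receive at least one dose of BAY 1895344 (elimusertib) will be evaluable for response". A responder needs a CR or PR confirmed by central review.
- Section 12.2 names RECIST 1.1 as the response standard and points to Appendix XIII for Ewing imaging guidance.

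**The concern.** A bone-based tumor with a soft-tissue mass of 10 mm or more on CT satisfies the first rule and is caught by the second. The text does not say which rule prevails.

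Three things follow. First, a site that applies the second rule must refuse Part B entry to a patient whose only disease is such a mass. Second, if the patient also has other measurable disease, the mass becomes non-target and its shrinkage stays outside the sum that decides PR. Third, a site and a central reader who each follow a different rule can reach opposite calls on the same scans.

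Response is the Phase 2 endpoint. B1 (Ewing sarcoma) is a primary-aim cohort that stops at 0 responses in 10 patients and needs 3 in 20, so one or two calls can change its conclusion. Under Sections 5.3.1 and 11.2.2, failing the B1 response requirement also closes a still-enrolling PK expansion to Ewing patients.

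**Working it through.** **1. Compare the text.** The sentence that lists bone lesions also lists abdominal masses, but only those not imaged by CT or MRI. The authors therefore used an imaging condition where they wanted one, and bone lesions have none. The note on cystic metastases restores measurability for one lesion type only. A soft-tissue component of a bone lesion is not mentioned anywhere in the supplied text.

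**2. Trace the literal reading.**

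| Situation | Entry to Part B | Scoring |
|---|---|---|
| Only disease is a bone-based mass of 10 mm or more on CT | Refused under 4.1.7.2 | Never in the denominator |
| Same patient, enrolled under the 10 mm rule, mass later refused as target | Enrolled | In the denominator; no PR possible; CR only if all disease disappears |
| Bone-based mass plus other measurable lesions | Enrolled | PR decided by the other lesions; the mass is recorded as present, absent or progressing |

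In the third row the error can run either way. Shrinkage of the bone-based mass earns nothing. But if the other targets shrink by 30%, the response table gives PR even when the bone-based mass is unchanged, because PR with persisting non-target disease is still PR.

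**3. Reproduce the B1 design (Section 11.5).** Stop at 0 of 10; effective at 3 or more of 20. With X1 and X2 each binomial(10, p):

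P(effective) = P(X1=1)·P(X2≥2) + P(X1=2)·P(X2≥1) + P(X1≥3)

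P(stop at stage 1) = (1−p)^10

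- p = 0.05: P(effective) = 0.0686; P(stop) = 0.599; expected size 10 + 0.401 × 10 = 14.0. The plan states 7%, 60% and 14.
- p = 0.25: 0.1877 × 0.7560 + 0.2816 × 0.9437 + 0.4744 = 0.882. The plan states 88%. P(stop) = 0.75^10 = 0.056.

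The plan's figures are correct.

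**4. Illustrate the second row only.** Let f be the fraction of true responses among enrolled B1 patients that cannot be scored. The scorable rate is 0.25 × (1−f). The documents give no value for f; the range is an assumption.

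| f | Scorable rate | Power | Stop at stage 1 |
|---|---|---|---|
| 0 | 25.0% | 88.2% | 5.6% |
| 10% | 22.5% | 82.9% | 7.8% |
| 20% | 20.0% | 75.9% | 10.7% |
| 30% | 17.5% | 66.9% | 14.6% |

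The table does not describe the first row, where the patient is refused entry, or the third, where PR can still be reached on other lesions.

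**The case against.** **The exclusion may cover only the osseous part.** The non-measurable bullet is framed as a residual class, covering whatever the measurable rule leaves over. On that view a mass measured at 10 mm or more on CT is already measurable, and the bone entry means disease within bone. This is a fair reading. A reader might infer that the appendix expressly bars every bone lesion, soft-tissue mass included; it contains no such sentence. The documents support an unresolved conflict, not an explicit bar.

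**RECIST 1.1 governs, and Ewing guidance is promised.** Section 12.2 says both. The guideline is not reproduced in full, so what it would settle cannot be judged here. The supplied appendix text shows no Ewing-specific imaging guidance, but some later pages are not in the supplied copy, so its absence from the full plan is not proven. Even so, Appendix XIII is where Section 12.2 sends its readers, and its two rules should agree.

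**The power loss does not follow from the literal reading.** This stands. Patients refused at entry never join the denominator, so power stays at 88%. The lower figures need patients enrolled under one rule and refused targets under the other, with no CR among them.

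**Unmeasured non-target disease is routine.** Also true: lesions beyond the fifth target are handled this way. But those are left out by a count limit, whereas here two definitions disagree on whether the lesion may be a target at all.

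**It is a conservative choice, and Part A takes evaluable disease.** Part A does lessen the effect on access for patients under 18. It does not help patients aged 18 or over, who can enter only Part B.

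**Conclusion.** The conflict within Appendix XIII is real and nothing in the supplied text resolves it. Read literally, it can keep a bone-based mass that is measurable on CT out of Part B or out of the PR sum. Patients with other measurable lesions can still have a PR on those, and CR remains possible if all disease disappears.

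Its size cannot be derived from the documents. They do not say how many B1 patients have bone-based disease, and the cohort also admits other EWS-fusion positive solid tumors. A reader might infer that B1 is really powered at 83%, 76% or 67%. The documents do not support that: those figures assume that 10%, 20% or 30% of true responses among enrolled patients go unscored because the masses are later refused as targets.

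The point is worth correcting because the disputed definition decides eligibility and the primary response endpoint in a cohort that needs only 3 responses in 20, and the correction is cheap.

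**What to change.** In Appendix XIII:

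1. In the non-measurable list, replace the unqualified entry for bone lesions with *bone lesions without a soft-tissue component measurable by CT or MRI*.
2. State that a soft-tissue component meeting the 10 mm limit is measurable and may be a target lesion, and that only this component is measured.
3. Add MRI to the 10 mm CT limit in the measurable-disease bullet, in line with the appendix's own acceptance of MRI.

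Give central review the same instruction. Make the change before target lesions are selected, because reclassifying lesions once responses are known would invite bias.

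The cost is a few wording changes in one appendix and a matching note to central review. No extra scans or patients are needed, and the two-stage design is unchanged. The drawback is that a soft-tissue margin is slightly harder to measure.
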